# **STUDY TITLE:**

# Comparison of Intraoperative Heart Rate and Respiratory Rate Acquired Via ATLASense Raphael PolyMonitor and Standard Intraoperative Monitors

### 1. STUDY AIM, BACKGROUND, AND DESIGN ABSTRACT

Vital signs are the objective foundation by which health care providers base clinical decisions. Thus, changes in vital signs serve as an important indicator of physiologic decline. To efficiently monitor for patient deterioration, we may benefit from technical innovation which improves upon traditional surveillance and reporting of these critical patient values. New remote monitoring technologies offer a method of obtaining continuous and comprehensive surveillance of patient vital signs, which can be transmitted to a remote working station for display and analysis . Indeed, investigation into the accuracy of wireless monitoring devices in reporting key parameters such as heart rate (HR) and respiratory rate (RR) as compared to traditional monitoring have shown some promising results .

The ATLASense RAPHAEL PolyMonitor is an investigational wearable and wireless patient monitoring device. The monitor can be attached to a patient's chest, and collect continuous physiological signals including HR, RR, skin temperature, body movement, as well as non-invasive blood pressure (NIBP) and transmit this information remotely for display and analysis. Ultimately, this PolyMonitor may be able to process multiple physiologic signals simultaneously for early detection and predictive modeling of patient physiologic deterioration, change the way alerts are transmitted to clinicians, reduce infection risk of multiple monitors reused on patients, and extend perioperative physiologic monitoring beyond the operating room and recovery areas to a patients home. While this monitor has significant potential to improve the efficiency of patient monitoring, it has yet to undergo validation studies.

In this observational comparison study, we aim to compare the HR and respiratory RR of intraoperative surgical patients simultaneously recorded by standard intraoperative monitors and the ATLASense RAPHAEL PolyMonitor. We also aim to determine degree of data loss, data gap duration, and validate the PolyMonitor alert system for tachycardia and bradycardia. Additional parameters of non-invasive blood pressure (NIBP) and body temperature will also be compared between the PolyMonitor and standard intraoperative

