#### **Data Collection**

The information that will be pulled from patient charts in EPIC is as follows:

Age Gender Race Height Weight Pregnancy status BMI Planned surgery and associated diagnosis Allergies

Co-morbidities ASA status

On the day of surgery, the ATLASense RAPHAEL PolyMonitor will be placed on the patient's left chest mid sternal line in the operating room by the anesthesia provider. Traditional physiologic monitors including the GE E-PSMP-00 Monitor/Datex Ohmeda Aisys CS2: EKG HR, Ventilator RR, End Tidal CO2 RR, blood pressure cuff, \*\*\* core temperature probe will also be placed on the patient in the operating room.

Data acquisition will include: HR, RR, NIBP, core body temperature, data loss events (instances when data was not recorded/saved for any reason by the polymonitor or other monitors) and duration of data gaps, bradycardic events, and tachycardic events. Acquisition of data from the ATLASense PolyMonitor will be confirmed after the device is applied. Data will initially by tracked via medical record number (MRN). Following data acquisition, subjects will be deidentified using a random number generator to assign data sets for further data tracking.

Data will be collected via the ATLASense system and through the traditional operating room monitors, and this data will be time matched through synchronization of the monitors post hoc. Data collection intervals will be every 1 minute starting prior to induction of anesthesia and ending at the time of intraoperative monitor removal in the operating room. The ATLASense PolyMonitor will be removed at the same time as traditional physiologic monitors.

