# ATLASense RAPHAEL PolyMonitor

The ATLASense RAPHAEL PolyMonitor is a small, non-intrusive, wireless, wearable multi-sensor device, attached to the patient's torso either with adhesive disposable patch or as a smart shirt. It continuously collects multiple physiological signals, analyzes them and transmits them to the ATLASense server. The PolyMonitor is composed of a rechargeable lithium polymer battery (3.6 Volts, 370 milliamp hour), an independent charger (5 volt input via mini USB/USB cable) which employs a universal 90-240 VAC 50/60 Hz to 5VDC converter and four FDA-approved hydrogel electrodes. The device has safe fault limit on electrical current which exceeds regulatory requirements.

The system enables monitoring a multiple array of physiological, postural and emotional parameters. For this study, the Heart rate (HR) and Respiration rate (RR) derived parameters will be calculated and updated every second, stored in internal memory, and transmitted. Measurements and alerts are transmitted via a low-power radio protocol (BT 4.2 Low Energy) to hotspots ("gateways" connected to the hospital communication network). The data is sent to ATLASense central server and to the healthcare service provider's server connected with the electronic medical record.

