# ATLASense RAPHAEL PolyMonitor – HR Detection

The electrocardiogram is recorded and processed to calculate the average HR by analyzing a single-lead electrocardiogram, which is preprocessed first to filter the raw electrocardiogram signal in order to minimize noise due to motion and muscle artifacts. Heart rate is measured using an algorithm developed by ATLASense.

The algorithm checks electrodes' contact to assure credibility, detects the R wave, computes several valid interbeat intervals, and computes the running HR with low latency. HR is calculated by computing inter-beat intervals (IBI), limiting IBI to one in every 300 mSec before the next beat (refractory period). The average HR is acquired by calculating the reciprocal of the average of 4 IBIs. Accuracy of resting HR is reported to be +/-1% or +/- 2 BPM, whichever is greater, and range of detection is reported to be from 30-240 BPM.

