### CARESCAPE™ Monitor B850 - HR Detection

This multiparameter high acuity patient monitor is intended for use in multiple areas within a health care facility. Within the perioperative setting it is indicated for monitoring of multiple different hemodynamic parameters. However, for our study we will be acquiring data from its ECG monitoring function, and calculated HR. The heart rate will be measured at 1 minute intervals and then compared with time-matched HR acquired through the ATLASense PolyMonitor.

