#### **Statistical Analysis**

The data pairs of HR and RR measurements obtained in 1-minute intervals derived from the wireless sensors and the traditional physiologic monitors will be analyzed using the Bland and Altman method for repeated measurements . The Bland and Altman method will also be used to account for within-subject variation by correcting for the differences across patients and the variance of differences between the average differences. The bias (mean difference) between the ATLASense RAPHAEL PolyMonitor sensors and reference monitor and the 95% limits of agreement (± 1.96 SD) will be determined for both HR and RR data.

PolyMonitor bradycardia and tachycardia alert notifications will be time matched with the HR measurements from the traditional monitor. Reliability in determining tachycardic and bradycardic events will be assessed by calculating sensitivity, specificity, positive predictive value and negative predictive value from paired data. True positive tachycardia will be defined as HR > 100 BPM via the traditional monitor. True positive bradycardia will be defined as HR < 60 BPM via the traditional monitor. Based on the data points from our primary aim (N=14303), we have 99% power to detect a change in sensitivity from 0.5 to 0.8 using a two-sided binomial test and 99% power to detect a change in specificity from 0.5 to 0.8 using a two-sided binomial test. The target significance level is 0.05. The prevalence of tachycardia and bradycardia is assumed to be 0.01 to  $0.02^{2,7}$ .

Data pairs for skin temperature and NIBP obtained in 1 to 5 minute intervals derived from the wireless sensors and the traditional physiologic monitors will be analyzed using the Bland and Altman method for repeated measurements . The Bland and Altman method will also be used to account for within-subject variation by correcting for the differences across patients and the variance of differences between the average differences. The bias (mean difference) between the ATLASense RAPHAEL PolyMonitor sensors and reference monitor and the 95% limits of agreement (± 1.96 SD) will be determined for both HR and RR data. Sample size calculation was estimated based on the primary study aim.

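### The alert analysis counts single 1-minute heart-rate readings, so it estimates per-minute classification and not the detection of tachycardic and bradycardic events that the plan names as its target

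*Combined protocol and SAP*

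**What the plan says.** Section 1 sets an aim to "validate the PolyMonitor alert system for tachycardia and bradycardia". In section 3, Statistical Analysis, the target is again events: "Reliability in determining tachycardic and bradycardic events will be assessed by calculating sensitivity, specificity, positive predictive value and negative predictive value from paired data".

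The elements of the comparison are these:

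- **Device side.** The alert notification, not the PolyMonitor heart-rate value: "PolyMonitor bradycardia and tachycardia alert notifications will be time matched with the HR measurements from the traditional monitor".
- **Reference side.** A single reading beyond a limit, for example "True positive tachycardia will be defined as HR > 100 BPM via the traditional monitor". Bradycardia is defined in the same way, below 60 BPM. No minimum duration is given.
- **Reference sampling.** "The heart rate will be measured at 1 minute intervals" (CARESCAPE Monitor B850 – HR Detection) and "Data collection intervals will be every 1 minute starting prior to induction of anesthesia" (Data Collection).
- **Device sampling.** "the Heart rate (HR) and Respiration rate (RR) derived parameters will be calculated and updated every second" (ATLASense RAPHAEL PolyMonitor).
- **Power.** 99% for sensitivity 0.5 versus 0.8, and likewise for specificity, by two-sided binomial test at 0.05, based on the 14,303 data points of the primary aim and an assumed prevalence of 0.01 to 0.02.

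The documents do not define an episode, a matching window, or how an alert counts for later minutes of the same episode. They give no heart-rate alert limit, delay or repeat rule. The only alert rule described is the one for respiratory rate.

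**The concern.** An event such as sustained bradycardia can cover many consecutive reference readings. A clinician asks whether the device alerted, and how soon. A table of minutes answers another question: in what share of abnormal minutes was an alert recorded? The two answers agree only if the alert is present in every minute of an episode or if episodes last one minute.

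Three things are at stake. First, sensitivity may depend on how often the device repeats a notification rather than on whether it detects the event. Second, one patient with a long episode contributes many positive units and can dominate the result. Third, the device updates every second while the reference is read once a minute. An alert for a true short excursion between two readings may therefore score as a false positive, depending on a matching window that is not stated.

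Because the matching and coding rules are open, two statisticians could build different 2×2 tables from the same data.

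**Working it through.** **Inputs from the documents.** N = 14,303 data points; prevalence 0.01 to 0.02; null 0.5 and alternative 0.8; two-sided alpha 0.05; 1-minute readings; procedures of 2–5 hours (Project Timeline). **Inputs not in the documents.** Mean episode length L and alert behaviour, shown below as a range and as alternatives.

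**Step 1: reproduce the stated power.**

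- Positive minutes: 14,303 × 0.01 = 143; 14,303 × 0.02 = 286.
- Negative minutes: 14,303 − 143 = 14,160; 14,303 − 286 = 14,017.
- The exact equal-tailed one-sample binomial test, 0.5 versus 0.8, has power above 0.9999 for sensitivity and specificity at both prevalences.

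The stated 99% holds as a floor when each 1-minute reading is the unit. This confirms the unit that the plan has in mind.

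**Step 2: a device that misses nothing, with one alert per episode (assumption).** Each episode of L minutes gives 1 alerted minute and L − 1 unalerted minutes, so per-minute sensitivity = 1/L. Event-level sensitivity is 100% in every row. Episodes = positive minutes / L, rounded down.

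| L (min) | Per-minute sensitivity | False-negative minutes of 143 | False-negative minutes of 286 |
|---|---|---|---|
| 1 | 100% | 0 | 0 |
| 2 | 50% | 72 | 143 |
| 3 | 33% | 96 | 191 |
| 5 | 20% | 115 | 229 |
| 10 | 10% | 129 | 258 |

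Sensitivity falls below 0.8 once L exceeds 1/0.8 = 1.25 minutes, and below the null of 0.5 once L exceeds 1/0.5 = 2 minutes.

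**Step 3: alert active in every minute (the other assumption).** All positive minutes of a detected episode are scored as detected, so the loss in step 2 is zero. Weighting by duration remains: an episode of 10 minutes counts ten times as much as one of 1 minute. As an extreme bound and not a forecast, 143 minutes is 143/60 = 2.4 hours and 286 minutes is 4.8 hours. Either total fits within a single procedure of 2–5 hours.

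**Step 4: power with the episode as the unit.** Same exact test, 0.5 versus 0.8, episodes treated as independent.

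| L (min) | Episodes, prevalence 0.01 | Power | Episodes, prevalence 0.02 | Power |
|---|---|---|---|---|
| 3 | 47 | 99% | 95 | >99% |
| 5 | 28 | 91% | 57 | >99% |
| 10 | 14 | 45% | 28 | 91% |

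The 99% carries over to events only if episodes are short: about 3 minutes on average at prevalence 0.01, or about 6 at 0.02. Episodes cluster within the planned 60–70 patients, and these figures make no allowance for that.

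**The case against.** The strongest reply is that the 1/L loss rests on device behaviour that nobody has described. A reader might infer that the analysis will count most abnormal minutes as missed. The documents do not support this. No section says that an alert is a one-off message, and a heart rate updated every second fits equally well with an alert that stays on through an episode. If every minute is a unit, each minute needs an alert status, and coding by status removes the loss. That objection stands: the 1/L figures are conditional, not a demonstrated bias.

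Other stronger readings also go too far:

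- A reader might infer that the alert itself works on four beats, because "The average HR is acquired by calculating the reciprocal of the average of 4 IBIs" (4 × 60/100 = 2.4 s at 100 BPM; 4 × 60/60 = 4 s at 60 BPM). That sentence describes the displayed heart rate. No heart-rate alert algorithm is given, so the false-positive mechanism rests only on the difference between 1-second and 1-minute sampling.
- A reader might take the 143 to 286 positive minutes as applying to each condition. The prevalence sentence does not say whether its range is for each condition or for both together.
- A reader might conclude that the 99% power is wrong. It reproduces, but for minutes.

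It can also be said that the Data Collection section lists bradycardic and tachycardic events as items to be acquired. It does, but it does not define them, and the Statistical Analysis section does not use them as the unit. Matching to every minute is not spelled out either, but the N, the prevalence and the specificity calculation all imply it. Finally, this is a secondary outcome, and the primary Bland–Altman analysis is untouched.

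**Conclusion.** The point holds as a mismatch between target and unit. The plan names events and the alert system, but the analysis and its power statement are built on single 1-minute readings. That is true whichever way the alert behaves.

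The size depends on what the documents leave open. With one alert per episode, perfect detection scores 50%, 20% and 10% at 2, 5 and 10 minutes. With an alert active throughout, nothing is lost, but the estimate is weighted by episode duration. For event detection, the stated 99% power becomes roughly 45% to above 99% over mean episode lengths of 3 to 10 minutes and prevalences of 0.01 to 0.02. This takes the prevalence as a share of minutes and treats episodes as independent.

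The change should be made. It does not bear on the primary outcome.

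**What to change.** In section 3, Statistical Analysis:

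1. **Make episode-level sensitivity and PPV the main event-detection result.** Define an episode as a run of consecutive reference readings above 100 or below 60 BPM. State how runs separated by short returns to the normal range are merged, and how gaps in either data stream are handled. Use one matching window, for example ±1 minute around the episode, for both purposes: an alert inside it is a detection, and an alert outside every such window is a false positive. Report the time from episode start to alert, so that a late alert is visible as late.
2. **Keep a per-minute 2×2 table for specificity and NPV.** Code each minute by alert state (active or not). If the log holds only notification times, write down when an alert is taken to end. Add a table by PolyMonitor heart-rate value as supplementary only, since it does not test the alert system.
3. **Document the PolyMonitor heart-rate alert limits and repeat behaviour.** Reconcile the limits with the 60 and 100 BPM reference definitions before the first case. The documents do not say whether the limits can be changed.
4. **Restate the power.** Label the 99% as a per-minute figure, give event-level power over a range of episode lengths as in the second table above, and use intervals that allow for clustering within patients. State whether the prevalence is for each condition or for both together.

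The cost is plan wording, a short data step on readings already collected, and a record of the device's alert settings. The downside is fewer units, wider intervals and a lower stated power for this secondary outcome.

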#### Project Timeline

The primary end-point of the study is the collection of 14,303 time-matched HR and RR data pairs to power the study for 95% level of agreement (N = 14,303). This would require approximately 238 hours of intraoperative data collection if 1-minute intervals are used for time-matched data pairs. We estimate that 60-70 patients will need to be recruited based on surgical procedures with anticipated durations of 2-5 hours. Data collection is estimated to take approximately 3 months. Data analysis, and manuscript preparation is estimated to take an additional 6 months.

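### No interval or within-patient method is stated for the alert metrics, and the only test named, in the power sentence, treats serial minutes as independent; the 99% sensitivity power is conditional on that

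*Combined protocol and SAP*

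**What the plan says.** Section 1 of the combined protocol and SAP lists among the aims to "validate the PolyMonitor alert system for tachycardia and bradycardia". Section 3, Study Design and Outcomes, makes detection of bradycardia and tachycardia a secondary outcome. Under Statistical Analysis, this outcome "will be assessed by calculating sensitivity, specificity, positive predictive value and negative predictive value from paired data". That sentence names no interval and no test.

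The only inferential method for the outcome is in the power statement, which starts from the 14,303 data points of the primary aim: "we have 99% power to detect a change in sensitivity from 0.5 to 0.8 using a two-sided binomial test". An identical claim follows for specificity, at a significance level of 0.05. The event rate is then given: "The prevalence of tachycardia and bradycardia is assumed to be 0.01 to" 0.02.

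On the structure of the data, Data Collection says "Data collection intervals will be every 1 minute starting prior to induction of anesthesia", and Project Timeline says "We estimate that 60-70 patients will need to be recruited based on surgical procedures with anticipated durations of 2-5 hours".

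For the agreement analyses the plan does recognise repeated measures: "The Bland and Altman method will also be used to account for within-subject variation by correcting for the differences across patients". This appears for heart rate and respiratory rate, and again for skin temperature and blood pressure. The alert paragraph lies between these two and has no counterpart.

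**The concern.** A binomial test on minutes takes each minute as a separate trial. Here about 204 to 238 consecutive minutes come from each patient, with one device placement per patient. Section 3 itself names device placement, surgical practices and positioning as matters that may affect data collection, and these act on whole patients. Neighbouring event minutes may also belong to one episode. Some within-patient correlation in whether the alert is right is therefore plausible, though the documents do not give its size.

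If the results are reported with binomial intervals, or tested against 0.5 on that basis, the alert system would usually look more precisely validated than the data allow. Sensitivity is the exposed metric. It rests on the few event minutes, and the plan does not say how many patients those may come from.

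**Working it through.** **Inputs from the documents.** 14,303 one-minute pairs; 0.5 against 0.8; two-sided binomial test at 0.05; prevalence 0.01-0.02 (Statistical Analysis). 60-70 patients (Project Timeline).

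**Assumed inputs.** ICC of alert correctness within a patient: 0.05 to 0.5 for sensitivity. Patients contributing event minutes: 6, 13, 32 or 65, that is, roughly a tenth, a fifth, half or all of 65.

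**Step 1: counts.** Minutes per patient: 14,303/70 = 204 to 14,303/60 = 238. Event minutes: 14,303 × 0.01 = 143 to 14,303 × 0.02 = 286. Non-event minutes: 14,160 to 14,017. For sensitivity the binomial n is therefore 143-286, not 14,303.

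**Step 2: the plan's own figure.** An exact two-sided binomial test of 0.5 against 0.8 has true size 0.044 (n = 143) or 0.038 (n = 286), and power above 99.99% in both cases. The 99% reproduces under independence. About 44-47 independent event minutes would be enough for 99%. If a prevalence of 0.01 were shared between the two event types (about 72 minutes each), power would still be 0.9997.

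**Step 3: coverage of an independent-minutes interval for sensitivity.** With m = 143/k event minutes in each of k patients, the design effect is DE = 1 + (m − 1) × ICC. A nominal 95% interval that ignores it covers about 2Φ(1.96/√DE) − 1. At ICC 0.2:

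| Patients with events | m | DE | Coverage by formula | Coverage simulated, true sensitivity 0.8 | Type I error of binomial test at 0.5, simulated |
|---|---|---|---|---|---|
| 6 | 23.8 | 5.57 | 59% | 59% | 40% |
| 13 | 11.0 | 3.00 | 74% | 75% | 25% |
| 32 | 4.47 | 1.69 | 87% | 87% | 12-13% |
| 65 | 2.20 | 1.24 | 92% | 92% | 7% |

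The simulation is beta-binomial with near-equal cluster sizes and Clopper-Pearson intervals. The independent-minutes half-width is about 7 points throughout. The clustered half-width is about 18-19, 12, 9 and 7.5 points in the same order.

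At ICC 0.05 coverage is 83, 90, 93 and 95%; at ICC 0.5 it is 41, 57, 76 and 88%. With events in 65 patients and ICC 0.01-0.03, the binomial test's type I error is 4.6-4.8%, so the error rate is not always inflated.

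**Step 4: sensitivity power with a patient-clustered test.** The test uses the pooled proportion, cluster-robust variance × k/(k − 1), and t with k − 1 degrees of freedom. With 143 event minutes evenly spread:

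| Patients with events | ICC 0.05 | ICC 0.1 | ICC 0.2 | ICC 0.5 |
|---|---|---|---|---|
| 6 | 98.8% | 93% | 78% | 51% |
| 13 | >99.9% | 99.9% | 98% | 85% |
| 32 or 65 | ≥99.5% | ≥99.5% | ≥99.5% | ≥99.5% |

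With 286 event minutes at ICC 0.2, power is 80% in 6 patients and 99% in 13. If 143 event minutes are spread unevenly over 32 patients (at least one each, the rest by Dirichlet(1) weights), power is 99.5% at ICC 0.2 and 94% at ICC 0.5.

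**Step 5: specificity.** At a true value of 0.8 the independent half-width is 1.96 × √(0.8 × 0.2/14,160) = 0.7 points. With 65 patients, m = 14,160/65 = 217.8. At ICC 0.01, DE = 1 + 216.8 × 0.01 = 3.17 and the half-width is 0.66 × √3.17 = 1.2 points. At ICC 0.05, DE = 11.8 and it is about 2.3 points. Clustered power stays at about 100%.

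PPV and NPV have the same structure, with alert and non-alert minutes as denominators. They were not sized.

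**The case against.** The strongest defence has four parts.

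- **The stated 99% is right on its own terms.** This stands. A reader might infer that the power claim is false or the study underpowered, but the documents do not support that. The figure reproduces, and with events spread over 60-70 patients a design-effect calculation keeps power at 0.998 or more even at ICC 1. The study size does not rest on the sentence either: "Sample size calculation was estimated based on the primary study aim".
- **The plan commits to no faulty interval or test.** This also stands: the alert analysis sentence promises only calculation. A reader might infer a planned invalid analysis, but what the text shows is an omission. Still, the power statement supplies a test, a null value and a significance level, so inference is contemplated and the binomial test is the only method on offer.
- **The large effects need events in few patients together with appreciable ICC, and no passage supports either.** True. With events in 65 patients and ICC up to 0.2, coverage is 92-95%. But the plan does not rule out the unfavourable case.
- **Clustered methods are themselves weak with few patients.** Also true. In 6 patients the simple clustered interval covers only 91% at ICC 0.2 and 84% at ICC 0.5. This limits the remedy but does not rescue the independence assumption.

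**Conclusion.** The point holds as a gap in the analysis plan that should be fixed. For the alert metrics the documents give no interval and no within-patient method, and the one test they name treats serial minutes as independent. Any interval or test built that way will usually be too narrow or reject too often. For sensitivity the effect ranges from negligible (many patients with events, low ICC) to serious (few patients, appreciable ICC). For specificity the absolute widening is small.

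The 99% sensitivity power is conditional, not wrong. It holds under independence, and under clustering (ICC up to 0.5) when events are spread fairly evenly over about 32 or more patients. It can drop when events sit in few patients, or are very unevenly spread, with appreciable ICC.

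A reader might take 14,303 as the number of trials behind the sensitivity claim. The plan's own prevalence makes it 143-286. All sizes here rest on assumed ICCs and event spreads and on exchangeable correlation within patients. Point estimates and specificity power are not in question.

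**What to change.** 1. State that sensitivity, specificity, PPV and NPV will be reported with patient-clustered 95% confidence intervals (a bootstrap that resamples patients, or GEE with small-sample robust variance). Any test against 0.5 should use the same basis.
2. Report how many patients contribute tachycardia and bradycardia minutes, and present sensitivity descriptively if only a handful do. In simulation with unevenly spread events, the simple clustered test rejects 9-17% of the time at a nominal 5% in 6 patients and 8-11% in 13, against 5-8% in 32 or 65.
3. Restate the 99% sensitivity power as assuming independent event minutes, and add a range over stated ICCs, low values included, and numbers of patients with events. The specificity power can stay.

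The cost is SAP wording and a few lines of code, with no extra patients. The downside is wider intervals and a less favourable stated power for sensitivity.

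### The alert outcome is powered against a specificity of 0.5, and at the plan's own 1–2% prevalence rejecting 0.5, or even reaching 0.8, says little about whether an alert can be believed

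*Combined protocol and SAP*

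**What the plan says.** Section 1 (Study Aim, Background, and Design Abstract) includes among its aims to "validate the PolyMonitor alert system for tachycardia and bradycardia". Under Study Design and Outcomes in section 3, reliability in detecting these events is a secondary outcome.

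The Statistical Analysis section matches alerts in time to the reference heart rate and assesses reliability by "calculating sensitivity, specificity, positive predictive value and negative predictive value from paired data". No acceptable level is given for any of the four measures. The numerical statements about the alert outcome are these:

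- for sensitivity, "99% power to detect a change in sensitivity from 0.5 to 0.8 using a two-sided binomial test";
- for specificity, "99% power to detect a change in specificity from 0.5 to 0.8 using a two-sided binomial test";
- both tests at a 5% significance level;
- events of either kind taken to have a prevalence between 0.01 and 0.02.

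Both power claims use the 14,303 data pairs of the primary aim. The hypothesised limits under Study Design and Outcomes (10%, 3 breaths/min, 5 beats/min) concern heart-rate and respiratory-rate agreement and do not apply to alerts.

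**The concern.** When 98% to 99% of readings contain no event, specificity largely decides whether an alert can be believed. A specificity of 0.5 means a false positive in every second event-free minute; a specificity of 0.8 means one in five. A test of 0.5 against 0.8 therefore separates two levels at both of which nearly all positive readings are false.

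The study could report a highly significant specificity result beside a PPV of a few percent. The plan does not say which of the two should carry the statement about reliability. Because the stated aim is validation, that should be settled before the data are seen.

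**Working it through.** **Inputs, all from the plan**

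- N = 14,303 paired readings at 1-minute intervals, so 14,303 / 60 = 238.4 h. Project Timeline agrees: "This would require approximately 238 hours of intraoperative data collection if 1-minute intervals are used for time-matched data pairs".
- Prevalence 0.01 to 0.02, null 0.5, alternative 0.8, two-sided alpha 0.05 (Statistical Analysis).
- Reading assumed here: prevalence is the share of 1-minute readings with an event. The plan states no unit, but using prevalence with N = 14,303 implies this one.

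**1. The plan's own figure.** Event readings are 14,303 × 0.01 = 143 or 14,303 × 0.02 = 286. Event-free readings are 14,160 or 14,017. An exact two-sided binomial test of 0.5 against 0.8, with readings taken as independent, has power above 99.99% for sensitivity and effectively 100% for specificity. The stated 99% is reproduced; the arithmetic of the power claim is not in question.

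**2. What 0.8 implies.** Formulas, with Se for sensitivity, Sp for specificity and p for prevalence:

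- PPV = Se·p / [Se·p + (1 − Sp)(1 − p)]
- false-positive minutes per hour = 60(1 − Sp)(1 − p)

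At Se = Sp = 0.8:

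| | p = 0.01 | p = 0.02 |
|---|---|---|
| True-positive minutes in 14,303 | 114 | 229 |
| False-positive minutes in 14,303 | 2,832 | 2,803 |
| False-positive minutes per hour | 60 × 0.2 × 0.99 = 11.9 | 60 × 0.2 × 0.98 = 11.8 |
| PPV | 0.008 / (0.008 + 0.198) = 3.9% | 0.016 / (0.016 + 0.196) = 7.5% |

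With perfect sensitivity and Sp = 0.8, PPV rises only to 4.8% (p = 0.01) or 9.3% (p = 0.02). The result does not depend on taking sensitivity as 0.8.

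**3. What rejecting 0.5 implies.** The smallest count of correct event-free readings that rejects 0.5 upwards is 7,198 of 14,160, a specificity of 0.508. The normal approximation agrees: 0.5 + 1.96 × √(0.25 / 14,160) = 0.508. At that specificity and Se = 0.8 there are about 29 false-positive minutes per hour, and PPV is 1.6% (p = 0.01) or 3.2% (p = 0.02).

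**4. What a stated PPV would need.** Solving the PPV formula for specificity gives Sp = 1 − Se·p(1 − PPV) / [PPV(1 − p)]. At Se = 0.8:

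| PPV target | Sp needed, p = 0.01 | Sp needed, p = 0.02 |
|---|---|---|
| 50% | 1 − 0.008/0.99 = 0.992 | 1 − 0.016/0.98 = 0.984 |
| 80% | 1 − 0.002/0.99 = 0.998 | 1 − 0.004/0.98 = 0.996 |

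A rounder value such as 0.98 is not enough for a PPV of 50%. It gives 0.008 / (0.008 + 0.0198) = 29% at p = 0.01 and 0.016 / (0.016 + 0.0196) = 45% at p = 0.02.

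**The case against.** The strongest reply is that 0.5 and 0.8 appear only in a power sentence, at a sample size fixed by the primary aim. A reader might infer that the plan would declare the alert reliable once 0.5 is rejected or 0.8 is reached. The documents do not support that: no such rule is written anywhere. This part of the reply stands. What remains is that the power sentence names the only hypothesis test for the alert and the only numerical target. If it is not the criterion, the plan has none.

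PPV is also already planned, so a low value would be visible beside the specificity. That is true and limits the harm. But PPV has no level to be judged against and no stated priority over the test.

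A reader might also take the figures as about 12 separate alarms an hour, or as a forecast for this device. They are neither. They count false-positive 1-minute readings; consecutive ones could form one alert, and the plan defines no episode. They describe what the benchmark would allow, not what the device will do: the HR Detection section reports a resting heart-rate accuracy of ±1% or ±2 BPM, and alert specificity may prove far above 0.8.

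Finally, the plan does not say whether prevalence applies to minutes or patients, or to each condition or both together. The figures above are for one alert type on the per-minute reading. If each alert type had a specificity of 0.8 at the stated prevalence, the two together could give up to about 24 false-positive minutes an hour (2 × 11.9).

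**Conclusion.** The point holds as a weakness in how a secondary outcome will be judged. A two-sided test of specificity against 0.5 cannot inform the reliability of an alert at 1–2% prevalence. It rejects at about 0.508, where PPV is 1.6–3.2%; even at the alternative of 0.8, PPV is 3.9–7.5% with about 12 false-positive minutes per hour.

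This rests on reading prevalence as a share of 1-minute readings and, for the PPV figures, on the plan's own sensitivity of 0.8. It does not rest on whether the minutes are independent. That is a separate question, although it affects the intervals and any restated power. The primary agreement analysis is unaffected.

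**What to change.** In the Statistical Analysis section:

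1. Replace the 0.5 null for specificity with a minimum derived from the stated prevalence and a PPV target chosen by the sponsor, using the formula in step 4 of the working. A PPV of 50% is only an example; it needs about 0.984 at 2% prevalence or 0.992 at 1%.
2. State that rejecting 0.5, for specificity or for sensitivity, will not be read as validation of the alert.
3. Base the reliability statement on PPV and false-positive minutes per monitored hour, for each alert type, with confidence intervals that allow for clustering by patient.
4. Say what unit the prevalence refers to, and whether it applies to each condition or to both together.

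The change needs no new patients or data. Its cost is that the 99% power statement for specificity must be withdrawn or restated against the stricter null. A restated figure should allow for clustering within the planned 60–70 patients, which needs an assumed within-patient correlation that the documents do not give. The device may also fail to meet the stricter minimum.
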